### 3.2 Study Groups

- Intervention group: Patients treated with FlowTriever®
- Comparison group: Patients treated with thrombolysis
- Intervention group with prior thrombolysis: a subgroup of the intervention group including patients that have received thrombolysis before FlowTriever®. They will be separately described and exploratively analyzed as an own intervention group within the study. No formal statistical comparisons will be made for this group.

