## 5.4 Intervention

Following variables related to the intervention of FlowTriever® will be summarized:

- Indication for intervention (e.g. contraindication to thrombolysis, unsuccessful thrombolysis, other indication)
- Contraindication to thrombolysis (none, trauma, surgery, ischemic stroke, hemorrhagic stroke, active bleeding, risk for bleeding, ongoing anticoagulation, other indication)
- Use of Cellsaver/FlowSaver™ or equivalent
- Rescue treatment after intervention (thrombolysis, surgical embolectomy, ECMO)
- ECMO during intervention (yes, no)
- Technical success (yes, no), defined as achievement of desirable catheter positioning, as assessed by the interventionist
- Procedural success (yes, no), defined as technical success with successful extraction of thrombus material in the absence of major complications, as assessed by the interventionist

- Clinical success (yes, no), defined as hemodynamic or respiratory improvement following intervention, including but not limited to: increase in SaO2, reduced FiO2, regress of hypotension/tachycardia/tachypnoea, reduced need for circulatory support.
- Complications during intervention (bleeding, perforation, other complication)
- Other complications (coded by ICD-10 if relevant)

Following variables related to the treatment with thrombolysis will be summarized:

- Dose of thrombolysis
- Duration of infusion of thrombolysis
- Reason for premature discontinuation of thrombolysis (when relevant)
- Contraindication for thrombolysis (if relevant)
- Rescue treatment after thrombolysis (surgical embolectomy, ECMO)

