## 5.5 Outcome Variables

### 5.5.1 Primary Outcome Variable

The primary variable in this study is the composite endpoint death at 30 days and/or severe bleeding (according to GUSTO bleeding criteria) within 7 days after treatment with the FlowTriever® device or contemporary thrombolysis.

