## 5.6 Confounders and Predictors

The confounders and predictors for the outcomes will be used in propensity scores and adjustments. All variables listed below will be included when building propensity scores. For the adjusted analyses, only the

strongest confounders and predictors will be part of the analyses. The number of confounders/predictors in the adjusted analyses will be based on the number of events available in the studied cohort. The general recommendation is to not have more than 1 variable/10 events in a statistical model. We will calculate the maximum number of variables in our study as N events/10.

The following variables will be investigated whether they are statistically defined confounders, i.e. related to both the intervention and the outcome:

- Contraindication for thrombolysis (8 categories)
- Insufficient previous effect of thrombolysis
- Cardiac arrest before treatment

The following variables will be investigated for their relation to the study outcomes:

- Age
- Sex
- Active cancer
- Invasive ventilation before treatment
- Circulatory instability
- Chronic heart failure
- Chronic pulmonary disease (COPD, asthma, other)
- Respiratory rate >30 beats/min
- Center

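### The SAP does not fix one primary comparison set: sections 3, 3.1 and 4.1 give different control windows, and section 3.2 leaves open whether FlowTriever patients with prior thrombolysis enter the primary regression

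*SAP*

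**What the plan says.** **Control window.** Three sections of the SAP describe when a control may have been treated.
- Section 3 (Study Design): while the device was in use at the same hospital.
- Section 3.1: from 1 January of the centre's introduction year to the end of 2023.
- Section 4.1: the calendar years 2021, 2022 and 2023 at every included centre. This is the FAS, and Table 4.1 in section 7 reports the main analysis on it.

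**Prior-thrombolysis patients.** Section 3.2 describes them as "a subgroup of the intervention group including patients that have received thrombolysis before FlowTriever". It continues: "They will be separately described and exploratively analyzed as an own intervention group within the study", and then "No formal statistical comparisons will be made for this group". The control arm is defined without an exclusion: "Comparison group: Patients treated with thrombolysis".

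Section 5.4 gives as a FlowTriever variable "Indication for intervention (e.g. contraindication to thrombolysis, unsuccessful thrombolysis, other indication". For the thrombolysis arm it gives "Rescue treatment after thrombolysis (surgical embolectomy, ECMO", a list that does not name FlowTriever. Section 5.5.1 counts severe bleeding "within 7 days after treatment with the FlowTriever® device or contemporary thrombolysis".

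**Propensity score.** Section 5.6 says "All variables listed below will be included when building propensity scores". The list includes a variable for insufficient effect of earlier thrombolysis. Section 6.5 carries out 1:1 matching only if at least 70% of FlowTriever patients find a match.

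**The concern.** Two analysts who both follow the SAP could analyse different patients. One would take controls from all of 2021-2023, the other only from each centre's introduction year. The extra controls in the first analysis were treated before the device was available at their hospital. They are non-concurrent, and any change in care or case mix over those years would enter the treatment contrast.

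The same analysts could differ on prior-thrombolysis patients. One would read the bar on formal comparisons as applying only to the separate subgroup display. The other would read it as removing these patients from the primary logistic regression, which is itself a formal comparison.

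The study is retrospective, so a choice left open now could be settled once outcomes are visible.

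**Working it through.** **1. Control window.** The inputs are sections 3, 3.1 and 4.1. Start dates are not in the SAP, so two are assumed for illustration. Months of eligible controls up to the end of 2023:

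| Assumed start | Section 3 | Section 3.1 | Section 4.1 |
|---|---|---|---|
| 1 July 2021 | 30 | 36 | 36 |
| 1 July 2022 | 18 | 24 | 36 |

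Sections 3.1 and 4.1 agree for a 2021 start and diverge for any later one. Section 3 is narrower than 3.1 for any centre that did not start on 1 January.

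**2. The plan's power figure.** Inputs from section 6.1: 60 FlowTriever patients, 200 controls, 20% versus 40%, two-sided Fisher's exact test, alpha 0.05. Power is the sum of Bin(x; n, 0.20) × Bin(y; 200, 0.40) over all tables (x, y) with Fisher p ≤ 0.05. For n = 60 this gives 82.7%, so the stated minimum of 80% reproduces.

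**3. Power if prior-thrombolysis patients are left out.** Their number is not given. The 200 controls and both event rates are kept:

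| Left out | n | Power |
|---|---|---|
| 0 | 60 | 82.7% |
| 4 | 56 | 80.2% |
| 5 | 55 | 79.3% |
| 6 | 54 | 78.4% |
| 12 | 48 | 75.4% |
| 18 | 42 | 67.9% |

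These figures are for the unadjusted test of 6.1. The primary analysis is adjusted.

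**4. Power if a narrower window yields fewer controls.** With 60 FlowTriever patients and assumed control counts, power is 82.3% at 180, 79.6% at 160 and 74.2% at 100.

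**5. Bleeding between the two treatments.** Section 6.1 implies 0.20 × 60 = 12 FlowTriever events. Assume 6, 12 or 18 prior-thrombolysis patients, of whom 0 to 10% bled severely before FlowTriever. The 10% is the Background section's figure for major bleeding, which is not the GUSTO severe category. Then at most 0.10 × 6 = 0.6, 0.10 × 12 = 1.2 or 0.10 × 18 = 1.8 events depend on where the clock starts.

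**6. Propensity score.** Suppose m FlowTriever patients are coded as failed thrombolysis and no control is. The fitted logit gap L between these patients and the rest then grows without limit. With p = m/260, the caliper of 0.2 SD of the logit tends to 0.2 × √(p(1−p)) × L. For m = 6, 12 and 18 that is 3%, 4% and 5% of the gap, so no control falls within it. At most 60 − m patients can be matched: 54 (90%), 48 (80%) or 42 (70%). With m = 19 the maximum is 41/60 = 68.3%, and the 70% rule cancels the matched analysis.

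A simulation agrees (60 versus 200, three normal covariates shifted by 0.4 SD, greedy 1:1 matching, 200 data sets per setting): no positive-coded patient was matched. The result depends on coding. If 5, 10 or 20 controls are also coded positive and m = 12, about 34%, 55% or 80% of the positive-coded FlowTriever patients find a match. If the prior-thrombolysis patients are excluded, the variable is close to constant.

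**The case against.** The best defence is that membership is nearly settled. Section 3.2 defines the intervention group by treatment with the device and calls these patients a subgroup of it. Section 4.1 takes all treated patients, and Table 4.1 uses the FAS. The indication in 5.4 and the covariate in 5.6 make sense only if they are included. The bar on comparisons can then be confined to the subgroup display. This is the more coherent reading, and it stands. But the SAP never states it, and calling these patients an intervention group of their own points the other way.

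Four stronger readings are tempting, and the SAP does not support them.
- **That these patients have no day 0.** Membership of the intervention group points to FlowTriever as the index treatment. What is missing is an explicit sentence, and a place for bleeds between the two treatments.
- **That the study is underpowered or 6.1 is wrong.** The figure reproduces. The loss in step 3 arises only if the patients are excluded, which is the less likely reading.
- **That the FAS admits minors or unverified PE.** Section 4.1 does not repeat those conditions, but section 3.1 sets eligibility and section 3 keeps unverified PE out of comparative analyses.
- **That the failed-thrombolysis covariate should leave the primary model.** Keeping these patients while dropping it would compare treatment failures with all controls, unadjusted for failure. The SAP names it as a possible confounder and only as a candidate for that model, so this is a trade-off.

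It is also fair that the propensity analyses are sensitivity analyses, and that the 70% rule and the drop-out analysis would reveal poor matching. Neither says how failed thrombolysis among controls is coded.

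On the window, section 3 may be read as narrative that 3.1 makes operational. That leaves the conflict between 3.1 and 4.1.

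**Conclusion.** The point holds as a defect of definition that should be fixed. The firmest part is the window: for any centre that introduced the device after 2021, 4.1 admits controls whom 3.1 excludes. How many cannot be computed, because start years are not given.

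The place of prior-thrombolysis patients is an unresolved ambiguity, with inclusion favoured. Its cost in power is nil if they are included. If they are excluded, power falls below 80% from five exclusions, at 6.1's rates and with 200 controls. The question of when their follow-up starts is small, at most 1.8 of 12 implied events under the assumptions shown.

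The propensity-score problem is conditional. It is complete if no control is coded as failed thrombolysis and partial if some are.

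**What to change.** 1. In section 4.1, define the FAS as patients who meet section 3.1, and use the same window in section 3. State in 6.1 which window the 200 controls were counted over.
2. In section 3.2, state that prior-thrombolysis patients are in the primary comparison, with follow-up counted from FlowTriever treatment. Limit the no-comparison sentence to their separate subgroup display. Report severe bleeds between the two treatments separately.
3. Add a sensitivity analysis of the primary outcome that excludes these patients. If the sponsor prefers to exclude them from the primary comparison, restate the power in 6.1.
4. In the analysis that excludes them, fit the propensity score without the failed-thrombolysis variable, and report that version alongside the planned one. Whether to drop the variable from the primary adjustment set is a separate trade-off and not part of this change.

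The cost is SAP wording and one extra sensitivity analysis with its own propensity score. For patients who had both treatments, the date of bleeding relative to each must be read from the records. Aligning the window may leave somewhat fewer controls.

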## 6 Statistical Methods

### 6.1 Sample Size

The few non-industry sponsored studies have been performed on a limited number of patients. Furthermore, there is an insufficiency of data concerning the outcomes in this particularly severe group of patients, making it challenging to make informed assumptions for a sample size calculation.

During the planned inclusion period, we anticipate enrolling 60 patients who will undergo the FlowTriever® procedure and 200 patients who will receive thrombolysis intervention. Assuming these group sizes and a 40% incidence rate of the composite outcome in the thrombolysis group, with a two-sided Fisher's exact test and an alpha level of 0.05, the FlowTriever® group would need to demonstrate a 50% reduction, equivalent to a 20% incidence of the composite outcome, to achieve a minimum of 80% statistical power. Our evaluation indicates that achieving such an outcome is feasible within the scope of this study, making it a viable candidate for a positive outcome.

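### Patients given thrombolysis and then FlowTriever count as intervention patients, so group membership depends on events after the first treatment, and the SAP does not say whether they enter the confirmatory comparison

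*SAP*

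**What the plan says.** Section 3.2 of the SAP has an intervention group (FlowTriever) and a comparison group (thrombolysis). Patients who had both, thrombolysis first, are "a subgroup of the intervention group including patients that have received thrombolysis before FlowTriever". The same section says that they will be described separately and explored as their own group, without formal comparisons.

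Such patients are expected. Section 5.4 records "Indication for intervention (e.g. contraindication to thrombolysis, unsuccessful thrombolysis, other indication". The rescue treatments it records after thrombolysis are surgical embolectomy and ECMO only, so FlowTriever after failed thrombolysis appears as a change of group and not as rescue.

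Section 5.5.1 counts the bleeding component of the primary outcome "within 7 days after treatment with the FlowTriever® device or contemporary thrombolysis". No section says which treatment starts the clock for a patient who had both.

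Three places suggest that switchers are in the main analysis:

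- Section 4.1 puts all treated patients in the full analysis set.
- Table 4.1 in Section 7 reports the main analysis of the primary outcome on that set.
- Section 5.6 lists insufficient effect of earlier thrombolysis as a candidate confounder, and every variable listed there goes into the propensity score.

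**The concern.** Group membership should be settled when follow-up starts. Here it depends on how a patient responded to thrombolysis and on whether the patient survived long enough to have a second procedure. The comparison group loses the failures who reached FlowTriever and keeps those who died before it.

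Neither treatment of switchers that the SAP leaves open removes this. If they are kept in the intervention group, failures of thrombolysis, and bleeding from the earlier lytic that falls within 7 days of the procedure, are counted under FlowTriever. If they are left out, the comparison group has still lost a selected part of the patients who started thrombolysis.

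The planned adjustment does not repair it. Failed earlier thrombolysis is itself a post-treatment event. It should be present almost only in the intervention group, so in a regression it acts much like exclusion, and in the propensity model it threatens separation. Both sensitivity analyses in Section 6.5 (propensity-score adjustment and 1:1 matching) use the same grouping. The primary outcome and the other three confirmatory outcomes in Section 6.2 are all affected.

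**Working it through.** **Step 1: the plan's own figure.** Section 6.1 states that "we anticipate enrolling 60 patients who will undergo the FlowTriever® procedure and 200 patients who will receive thrombolysis intervention". It assumes "a 40% incidence rate of the composite outcome in the thrombolysis group" and a FlowTriever rate "equivalent to a 20% incidence of the composite outcome", with a "two-sided Fisher's exact test and an alpha level of 0.05", "to achieve a minimum of 80% statistical power". Full enumeration of the exact test for 60 vs 200 patients at 20% vs 40% gives 82.7%. The statement holds on its own inputs and is not in dispute.

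**Step 2: set-up of the illustration.** The SAP gives neither the number of switchers, k, nor their composite risk, q. I assume k = 10 to 20 of the 60 and q = 30% to 60%. Then 200 + k patients start with thrombolysis at an overall risk of 40%, and 60 − k start with FlowTriever at risk p. The rates are crude.

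- Observed comparison rate: (0.40 × (200 + k) − q × k) / 200
- Observed intervention rate, switchers kept: (p × (60 − k) + q × k) / 60
- Observed intervention rate, switchers left out: p

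**Step 3: no true effect (p = 40%, true odds ratio 1.00).**

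| k | q | Kept: FlowTriever vs thrombolysis | OR kept | OR left out |
|---|---|---|---|---|
| 10 | 30% | 38.3% vs 40.5% | 0.91 | 0.98 |
| 20 | 30% | 36.7% vs 41.0% | 0.83 | 0.96 |
| 10 or 20 | 40% | 40.0% vs 40.0% | 1.00 | 1.00 |
| 10 | 50% | 41.7% vs 39.5% | 1.09 | 1.02 |
| 20 | 60% | 46.7% vs 38.0% | 1.43 | 1.09 |

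Worked line for k = 20, q = 60%: the comparison rate is (0.40 × 220 − 0.60 × 20)/200 = 76/200 = 38.0%. The intervention rate is (0.40 × 40 + 0.60 × 20)/60 = 28/60 = 46.7%. The odds ratio is (0.467/0.533)/(0.380/0.620) = 1.43.

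The sign turns at q = 40%. Below it the distortion favours FlowTriever, above it thrombolysis.

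**Step 4: the planned effect (p = 20%, true odds ratio 0.25/0.667 = 0.375).**

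| k | q | Kept: FlowTriever vs thrombolysis | OR kept | OR left out |
|---|---|---|---|---|
| 10 | 50% | 25.0% vs 39.5% | 0.51 | 0.38 |
| 20 | 60% | 33.3% vs 38.0% | 0.82 | 0.41 |

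If switchers are kept, crude Fisher power in these two rows is 52.1% and 8.6%.

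**Step 5: grouping by first treatment.** All 200 + k thrombolysis starters are then in the comparison group at 40%, and all 60 − k FlowTriever starters are in the intervention group at p. The odds ratio equals its true value for every k and q, so this mechanism is gone. Fisher power at 20% vs 40% becomes:

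| Switchers assumed | Group sizes | Power |
|---|---|---|
| 0 | 60 vs 200 | 82.7% |
| 6 | 54 vs 206 | 79% |
| 10 | 50 vs 210 | 77% |
| 20 | 40 vs 220 | 68% |

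**The case against.** **Section 3.2 may already keep switchers out.** It calls them a group of their own and rules out formal comparisons. On that reading the bias is small: 0.96 to 1.09 with no effect, and 0.38 to 0.41 against 0.375 with the planned effect at 50% to 60% switcher risk. This is a fair reading, and it limits the size of the point. It is not the only one, because Sections 4.1, 5.6 and 7 point the other way, and leaving switchers out still removes a selected part of the thrombolysis starters.

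**The illustration is crude, while the primary analysis is adjusted.** This stands. If failed earlier thrombolysis enters the model, the result moves towards the left-out figures. The kept figures are therefore an outer range and not a forecast of the planned analysis.

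**Stronger readings that the SAP does not support.**

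- A reader might infer that the comparison is biased however switchers are handled. It is not: grouping by first treatment removes this mechanism. Even under the present grouping, the bias with no true effect is zero if q equals 40%.
- A reader might infer that the bias runs against FlowTriever, or that power falls to about 9%. The direction depends on a switcher risk that the SAP does not give. The 9% is the worst corner (k = 20, q = 60%) of the kept reading.
- A reader might infer that the hypothesis is about first-line treatment. Section 2 compares patients treated with one or the other and does not say first-line, and Section 1 describes catheter intervention also after failed thrombolysis. Making first-treatment grouping primary is sound, but it is a choice open to debate.

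**Conclusion.** The concern holds in a limited form. Membership of both groups depends on response and survival after thrombolysis, and the SAP contradicts itself on whether switchers enter the confirmatory comparison. Under the present grouping the comparison is generally biased whether they are kept or left out. The bias can be material if they are kept and is modest if they are left out. All of these sizes rest on the assumed number and risk of switchers and on unadjusted rates, so the SAP alone settles neither direction nor size. The sample-size statement is correct on its own inputs. The change is worth making because it is specific and removes this mechanism, but nothing here shows that the study's result would be reversed.

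**What to change.** 1. In Sections 3.2 and 6.5, state whether switchers are in the confirmatory comparison, and bring Section 4.1 and Table 4.1 into line.
2. For the primary and other confirmatory comparisons, define the groups by the first reperfusion treatment given, with time zero at its start. FlowTriever after thrombolysis is then recorded as a subsequent treatment within the thrombolysis group.
3. For that analysis, drop insufficient effect of earlier thrombolysis from the adjustment and propensity models.
4. If the sponsor keeps the present grouping as primary, add the first-treatment grouping as a prespecified sensitivity analysis in Section 6.5 and Table 4.1.
5. Keep the separate description of the sequential group.

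The cost is SAP wording, one more run, and the loss of power shown in Step 5. Baseline values, which Section 5.1 takes from the 24 hours before intervention, and the outcome windows must be re-anchored to the first treatment for switchers, which may need some further record review. Confounding by indication remains and needs the planned adjustment in any case.

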## 4 Study Populations

### 4.1 Full Analysis Set

The full analysis set (FAS) will include all patients treated with FlowTriever® and thrombolysis at the included centers during the years 2021, 2022 and 2023.

## 5 Study Variables

### 5.1 Baseline Characteristics Variables

Following baseline characteristics will be collected and described:

- Age
- Sex (male, female)
- Mechanical ventilation (yes, no)
- Maximum heart rate (0-24 hours before intervention)
- Minimum systolic blood pressure (0-24 hours before intervention)
- Maximum respiratory frequency (0-24 hours before intervention)
- Maximum lactate levels (0-24 hours before intervention)
- Maximum cardiac troponin levels (0-24 hours before intervention)
- Maximum NT-proBNP levels (0-24 hours before intervention)

### 5.2 Medical History Variables

Following medical history variables will be collected and described:

- Hypertension (yes, no)
- Ischemic heart disease (yes, no)
- Heart failure (yes, no)
- Diabetes (yes, no)

- Chronic obstructive lung disease (yes, no)
- Asthma (yes, no)
- Other lung disease (yes, no)
- Previous stroke (yes, no)
- Liver disease (yes, no)
- Renal disease (yes, no)
- Active cancer (yes, no)
- Previous venous thromboembolism (yes, no)
- Symptomatic COVID-19 infection in the three months prior to intervention (yes, no)
- Other (coded by ICD-10 codes if relevant)

